5.7 Study Drug

ABBV-154 and matching placebo will be manufactured and provided by AbbVie (Table 2). Each dose will be administered by a healthcare professional either intravenously or as a subcutaneous injection in the abdomen or thigh. Blinded study drug will be administered at approximately the same time of day, preferably between 7 am and 11 am, beginning at the Baseline Visit (Week 0, Day 1) of each period. The study drug can be taken with or without food. Refer to Section 6.2 for required observation periods after each IV and SC doses. The last dose of study drug will be given at Week 38 of the Maintenance Period.

ABBV-154 and matching placebo syringes and vials will be packaged in cartons with quantities sufficient to accommodate the study design. Each pre-filled syringe (PFS), vial, and carton will be labeled per local requirements and these labels must remain affixed to the syringe, vial, and carton. Each kit will contain a unique kit number. This kit number is assigned to a subject via Interactive response technology (IRT) and encodes the appropriate study drug to be dispensed at the subject's corresponding study visit. Study drug must not be dispensed without contacting the IRT system. Site staff will complete all blank spaces on the label before dispensing study drug for the subject. Study drug is for investigational use only and will only be used for the conduct of this study.

Upon completion of or discontinuation from study treatment, all original study drug units (containing unused study drugs) will be returned to the sponsor (or designee) or destroyed on site. All return or destruction procedures will be according to instructions from the sponsor and according to local regulations following completion of drug/device accountability procedures.

Table 2. Investigational Product

Study Drug	Dosage Form	Strength	Route of Administration	Manufacturer
ABBV-154	Lyophilized powder for solution for infusion in vials	50 mg (50 mg/mL when reconstituted with 1.2 mL of sterile water for injection)	Intravenous	AbbVie
Matching Placebo	Lyophilized powder for solution for infusion in vials	N/A	Intravenous	AbbVie
ABBV-154	0.8 mL, 1.5 mL solution for injection in PFS	100mg/ml	SC Injection in abdomen or thigh	AbbVie
Matching Placebo	Placebo solution for injection in PFS	N/A	SC Injection in abdomen or thigh	AbbVie

N/A = not applicable; PFS = prefilled syringe; SC = subcutaneous

5.8 Randomization/Drug Assignment

All subjects will be assigned a unique identification number by the IRT at the screening visit. For subjects who rescreen, the screening number assigned by the IRT at the initial screening visit should be used. The IRT will assign a randomization number that will encode the subject's treatment group

assignment according to the randomization schedule. Randomization into the 12-Week Double-Blind Induction Period, the 12-Week Double-Blind Re-Induction Period, and the 40-Week Double-Blind Maintenance Period is outlined in Section 4.1.

Randomization at Baseline (Week 0, Day 1) of the Induction Period will be stratified as follows:

- Baseline glucocorticoid use (yes/no);
- Endoscopic disease severity (SES-CD < 15; SES-CD ≥ 15); and
- Inadequate response to adalimumab (yes/no).

Re-randomization at Baseline (Week 0, Day 1) of the Re-Induction Period will be stratified as follows:

- Treatment group in the Induction Period

Re-randomization at Baseline (Week 0, Day 1) of the Maintenance Period will be stratified as follows:

- Achievement of CR100 at entry of the Maintenance Period (Week 12 of the Induction/Re-Induction Period)
- For subjects who enter from the Induction Period: ABBV-154 dose groups in the Induction Period
- For subjects who enter from Re-Induction Period:
 - ABBV-154 dose groups in the Re-Induction Period
 - Induction Period treatment: ABBV-154 (any dose group) versus placebo

All AbbVie personnel with direct oversight of the conduct and management of the trial (with the exception of AbbVie Drug Supply Management Team) will remain blinded to each subject's treatment-assignment in each study period until the Primary Analysis of the respective period. The investigator, study site personnel, and the subject will remain blinded to each subject's assignment throughout the study. Selected AbbVie personnel may be unblinded to treatment assignment after an interim analysis to support regulatory interactions; details will be included in the interim unblinding plan (IUP). To maintain the blind, the ABBV-154 and placebo PFS and vials provided for the study will be identical in appearance. The IRT will provide access to unblinded subject treatment information in the case of a medical emergency.

In the event of a medical emergency that requires unblinding of the study drug assignment, the investigator is requested to contact the AbbVie TA MD prior to breaking the blind. However, if an urgent therapeutic intervention is necessary which warrants breaking the blind prior to contacting the AbbVie TA MD, the investigator can directly access the IRT system to break the blind without AbbVie notification or agreement. Unblinding is available in the IRT system via the Subject Unblinding by Site transaction, which is available only to the investigator. If the IRT system is unavailable, unblinding may occur by contacting the technical support of the IRT vendor via either phone (preferred) or email ([contact]). For country-specific phone numbers, please see the following website: <http://www.endpointclinical.com/help-desk>. In the event the blind is broken before notification to the AbbVie TA MD, the AbbVie TA MD should be notified within 24 hours of the blind being broken. The

date and reason that the blind was broken must be conveyed to AbbVie and recorded on appropriate eCRF.

5.9 Protocol Deviations

AbbVie does not allow intentional/prospective deviations from the protocol except when necessary to eliminate an immediate hazard to study subjects. The investigator is responsible for complying with all protocol requirements, written instructions, and applicable laws regarding protocol deviations. If a protocol deviation occurs (or is identified including those that may be due to the COVID-19 pandemic), the investigator is responsible for notifying independent ethics committee (IEC)/independent review board (IRB), regulatory authorities (as applicable), and AbbVie.

5.10 Data Monitoring Committee

An external DMC will be established to safeguard the interest of trial subjects by assessing the safety of the interventions during the trial as well as for monitoring of the integrity and interpretability of the trial. A separate DMC charter will be prepared outside of the protocol and will further describe the roles and responsibilities of the DMC members, frequency, and scope of the data reviews, and expectations for blinded communications. The first DMC review of unblinded safety data will occur after approximately 30 subjects (6 subjects/treatment group) have reached Week 8. The DMC will be requested to review the unblinded safety data at an earlier timepoint if the sponsor notes on blinded data review any of the following:

- Fatal or life-threatening event considered to have a reasonable possibility of being related to study drug by the investigator or sponsor;
- Serious hypersensitivity reaction considered to have a reasonable possibility of being related to study drug by the investigator or sponsor;
- Higher than anticipated rate of serious infection as compared to the rate for serious infection in subjects with CD receiving adalimumab in the Humira clinical trials.

5.11 Glucocorticoid Adjudication Committee

An independent adjudication committee will be established to adjudicate systemic glucocorticoid AEs. A separate charter will be prepared outside of the protocol and will describe the roles and responsibilities of the adjudication committee members, frequency of data reviews, and expectations for blinded communications.

6 SAFETY CONSIDERATIONS

6.1 Complaints and Adverse Events

Complaints

A complaint is any written, electronic, or oral communication that alleges deficiencies related to the physical characteristics, identity, quality, purity, potency, durability, reliability, safety, effectiveness, or performance of a product/device. Complaints associated with any component of this investigational product must be reported to AbbVie.

Product Complaint

A product complaint is any complaint related to the biologic or drug component of the product or to the medical device component(s).

For a product this may include, but is not limited to, damaged/broken product or packaging, product appearance whose color/markings do not match the labeling, labeling discrepancies/inadequacies in the labeling/instructions (e.g., printing illegible), missing components/product, device damage or not working properly, or packaging issues.

Product complaints concerning the investigational product and/or device must be reported to AbbVie within 24 hours of the study site's knowledge of the event.

Product complaints occurring during the study will be followed up to a satisfactory conclusion.

Medical Complaints/ Adverse Events and Serious Adverse Events

An adverse event is defined as any untoward medical occurrence in a subject or clinical investigation subject administered a pharmaceutical product and which does not necessarily have a causal relationship with this treatment. An adverse event can therefore be any unfavorable and unintended sign (including an abnormal laboratory finding), symptom, or disease temporally associated with the use of a medicinal (investigational) product, whether or not the event is considered causally related to the use of the product.

Such an event can result from use of the drug as stipulated in the protocol or labeling, as well as from "special situations" such as accidental or intentional overdose, medication error, occupational or accidental exposure, off-label use, drug abuse, drug misuse, or drug withdrawal, all which must be reported whether associated with an adverse event or not. Any worsening of a pre-existing condition or illness is considered an adverse event. Worsening in severity of a reported adverse event should be reported as a new adverse event. Laboratory abnormalities and changes in vital signs are considered to be adverse events only if they result in discontinuation from the study, necessitate therapeutic medical intervention, meets protocol-specific criteria (see Section 6.2 regarding toxicity management), and/or if the investigator considers them to be adverse events.

The investigators will monitor each subject for clinical and laboratory evidence of adverse events on a routine basis throughout the study. All adverse events will be followed to a satisfactory conclusion.

An elective surgery/procedure scheduled to occur during a study will not be considered an adverse event if the surgery/procedure is being performed for a pre-existing condition and/or the surgery/procedure has been pre-planned prior to study entry. However, if the pre-existing condition deteriorates unexpectedly during the study (e.g., surgery performed earlier than planned), then the deterioration of the condition for which the elective surgery/procedure is being done will be considered an adverse event.

Expected manifestations of CD that do not constitute worsening of the underlying condition are not to be recorded as AEs unless the event results in a serious outcome.

If any of the following events are reported, then the following supplemental report must be completed.

Event	Supplemental Report
Cardiac events Myocardial infarction or unstable angina Heart failure Cerebral vascular accident and transient ischemic attack Cardiovascular procedures (SAE Supplemental Procedure eCRF)	MACE eCRF
Discontinuation or interruption of study drug due to a hepatic-related AE A hepatic-related SAE Confirmed ALT/AST > 3 × ULN	Hepatic eCRF
Renal impairment Renal dysfunction Renal failure Confirmed serum creatinine >1.5 × the baseline value (of the Induction Period) and > ULN	Renal eCRF
Adrenal insufficiency	Adrenal insufficiency eCRF
COVID-19 infection	COVID-19 eCRF
Hypersensitivity Reaction	Hypersensitivity reaction eCRF

ALT = alanine aminotransferase; AST = aspartate transaminase; eCRF = electronic case report form; COVID-19 = coronavirus pandemic 2019; MACE = major adverse cardiac event; SAE = serious adverse event; ULN = upper limit of normal

If an adverse event, whether associated with study drug or not, meets any of the following criteria, it is to be reported to AbbVie clinical pharmacovigilance or contract research organization (as appropriate) as a serious adverse event within 24 hours of the site being made aware of the serious adverse event (refer to Section 4.2 of the Operations Manual for reporting details and contact information):

Death of Subject	An event that results in the death of a subject.
Life-Threatening	An event that, in the opinion of the investigator, would have resulted in immediate fatality if medical intervention had not been taken. This does not include an event that would have been fatal if it had occurred in a more severe form.
Hospitalization or Prolongation of Hospitalization	An event that results in an admission to the hospital for any length of time or prolongs the subject's hospital stay. This does not include an emergency room visit or admission to an outpatient facility.
Congenital Anomaly	An anomaly detected at or after birth, or any anomaly that results in fetal loss.
Persistent or Significant Disability/Incapacity	An event that results in a condition that substantially interferes with the activities of daily living of a study subject. Disability is not intended to include experiences of relatively minor medical significance such as headache, nausea, vomiting, diarrhea, influenza, and accidental trauma (e.g., sprained ankle).
Important Medical Event Requiring Medical or Surgical Intervention to Prevent Serious Outcome	An important medical event that may not be immediately life-threatening or result in death or hospitalization, but based on medical judgment may jeopardize the subject and may require medical or surgical intervention to prevent any of the outcomes listed above (i.e., death of subject, life threatening, hospitalization, prolongation of hospitalization, congenital anomaly, or persistent or significant disability/incapacity). Additionally, any elective or spontaneous abortion or stillbirth is considered an important medical event. Examples of such events include allergic bronchospasm requiring intensive treatment in an emergency room or at home, blood dyscrasias or convulsions that do not result in inpatient hospitalization, or the development of drug dependency or drug abuse.

All adverse events reported from the time of study drug administration until 70 days after discontinuation of study drug administration will be collected, whether solicited or spontaneously reported by the subject. In addition, study procedure-related serious and nonserious adverse events will be collected from the time the subject signs the study-specific informed consent.

The following definitions will be used for Serious Adverse Reactions (SARs) and Suspected Unexpected Serious Adverse Reaction (SUSAR):

SAR	Defined as all noxious and unintended responses to an Investigational Medicinal Product (IMP) related to any dose administered that result in an SAE as defined above.
SUSAR	Refers to individual SAE case reports from clinical trials where a causal relationship between the SAE and the IMP was suspected by either the sponsor or the investigator, is unexpected (not listed in the applicable Reference Safety Information), and meets one of the above serious criteria.

AbbVie will be responsible for Suspected Unexpected Serious Adverse Reactions (SUSAR) reporting for the Investigational Medicinal Product (IMP) in accordance with global and local requirements.

Adverse events will be monitored throughout the study to identify any safety topics of interest that may indicate a trend or risk to subjects.

Safety Topics of Interest

The following Safety Topics of Interest will be monitored during the study:

- Serious infections;
- Opportunistic infections;
- Active TB;
- Hypersensitivity reactions;
- Serious allergic reactions;
- Malignancies;
- Systemic glucocorticoid side effects;
- Adrenal insufficiency;
- Iatrogenic Cushing's syndrome.

Adverse Event Severity and Relationship to Study Drug

The investigator will rate the severity of each adverse event according to the National Cancer Institute Common Terminology Criteria for Adverse Events (NCI CTCAE Version 5.0), which can be accessed at: https://ctep.cancer.gov/protocoldevelopment/electronic_applications/docs/CTCAE_v5_Quick_Reference_5x7.pdf.

The investigator will use the following definitions to assess the relationship of the adverse event to the use of study drug:

Reasonable Possibility	After consideration of factors including timing of the event, biologic plausibility, clinical judgment, and potential alternative causes, there is sufficient evidence (information) to suggest a causal relationship.
No Reasonable Possibility	After consideration of factors including timing of the event, biologic plausibility, clinical judgment, and potential alternative causes, there is insufficient evidence (information) to suggest a causal relationship.

Pregnancy

While not an adverse event, pregnancy in a study subject must be reported to AbbVie within 24 hours after the site becomes aware of the pregnancy. Subjects who become pregnant during the study must be discontinued (Section 5.5). If a pregnancy occurs in a study subject or in the partner of a study subject, information regarding the pregnancy and the outcome will be collected.

In the event of pregnancy occurring in a subject's partner during the study, written informed consent from the partner must be obtained prior to collection of any such information. AbbVie will provide a separate consent form for this purpose. Pregnancy in a subject's partner will be collected from the date of the first dose through 70 days following the last dose of study drug.

The pregnancy outcome of an elective or spontaneous abortion, stillbirth or congenital anomaly is considered a SAE and must be reported to AbbVie within 24 hours after the site becomes aware of the event.

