10.2.2 Adverse Event Overview

An overview of AEs will be presented consisting of the number and percentage of subjects experiencing at least one event for each of the following AE categories:

- Any TEAE
- Any TEAE related to COVID-19
- Any TEAE that was rated as with reasonable possibility to study drug by the investigator.
- Any TEAE with CTCAE grade ≥ 3
- Any serious TEAE.
- Any TEAE leading to discontinuation of study drug.
- Any TEAE leading to death.
- Treatment-emergent AESI (See ABBV-154 Product Safety SAP (PSSAP) for details).
- All deaths
 - Deaths occurring ≤ 70 days after last dose of study drug
 - Deaths occurring > 70 days after last dose of study drug
 - Deaths related to COVID-19

In addition, an overview of AEs per 100 patient-years of study exposure will be presented for the AE categories defined above. The number of TEAEs reported, the total number of years of study drug exposure, and the TEAE rate per 100 patient-years will be presented.

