10.2.4 Treatment-Emergent Adverse Events per Patient-Years of Exposure

TEAEs will be summarized by event rate per 100 subject years, defined as

$$100 \times \frac{\text{Number of TEAEs}}{\text{Total Patient Years}}$$

where total patient years is defined as the sum of the study drug exposure of all subjects, normalized by 365.25, and rounded to 1 decimal place. Note that one event per preferred term per day per subject will be counted in the calculation of the number of AEs (i.e., a preferred term will not be counted twice on the same day for the same subject).

The TEAE rates per 100 patient-years of exposure will be provided for each AE category in the AE overview summary (defined in Section 10.2.2) and for TEAE summary by SOC and PT.

The study drug exposure for each safety population is defined as last dose date plus 70 days, minus the first dose date. For SA-All154 safety population, the duration when subjects on Placebo will not be included in the calculation.

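### One adverse event that worsens on later days is counted once per grade step in the any-TEAE, SOC/PT and non-adjudicated AESI rates per 100 patient-years

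*Protocol*

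**What the plan says.** **Recording.** Protocol 6.1 states: "Worsening in severity of a reported adverse event should be reported as a new adverse event". The same section ties severity to a graded scale: "The investigator will rate the severity of each adverse event according to the National Cancer Institute Common Terminology Criteria for Adverse Events". A worsening in severity is therefore a rise in CTCAE grade, and it produces a further AE record.

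**Counting for rates.** SAP 10.2.4 divides the number of TEAEs by total patient-years and multiplies by 100. Its one rule against double counting is that "one event per preferred term per day per subject will be counted in the calculation of the number of AEs", which it explains as meaning that "a preferred term will not be counted twice on the same day for the same subject". No text in the SAP joins records that start on different days.

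**Where the rates appear.** SAP 10.2.4: "The TEAE rates per 100 patient-years of exposure will be provided for each AE category in the AE overview summary". It adds the SOC/PT summary, and SAP 10.2.6 adds each AESI. For the overview, SAP 10.2.2 says: "The number of TEAEs reported, the total number of years of study drug exposure, and the TEAE rate per 100 patient-years will be presented". Some overview categories are restricted, for example "Any TEAE with CTCAE grade ≥ 3" and "Any TEAE leading to death".

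**Counting for percentages.** SAP 10.2 and 10.2.3 count each subject once per specific AE when percentages are calculated, and show the highest grade when an event recurs in a subject. These are subject-level rules. They do not say that records are merged in the rate numerator.

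**The concern.** The event rate is the SAP's only exposure-adjusted AE measure, and safety is part of the primary objective. A reader will take the rate as a frequency of events. As defined, it counts episodes plus later-day rises in grade, so it mixes how often events occur with how they develop. Two arms with the same number of episodes can show different rates because episodes worsen more often in one of them. Where AESI counts are small, a single subject can supply several events.

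The same-day rule shows that the SAP intends to avoid double counting, but it does not reach the double counting that Protocol 6.1 creates.

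**Working it through.** The documents give no AE count, AE rate or share of events that worsen, so there is no plan figure to reproduce. The check applies the SAP 10.2.4 rule to example records created under Protocol 6.1, then shows how the rate depends on the unknown share.

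**Step 1. Counts for one subject and one preferred term** (distinct start days among qualifying records):

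| Course of one episode | Any-TEAE rate | Grade 3 or higher rate |
|---|---|---|
| Grade 1 day 10, Grade 2 day 17, Grade 3 day 24 | 3 | 1 |
| Grade 2 day 10, Grade 3 day 17 | 2 | 1 |
| Grade 3 day 10, Grade 4 day 12 | 2 | 2 |
| Grades 1, 2 and 3 all starting day 10 | 1 | 1 |

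The SOC/PT rates follow the any-TEAE column, as do AESI rates for terms found by a MedDRA query. A restricted category takes only the records that meet its criterion. Non-fatal records do not enter the category of TEAEs leading to death.

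**Step 2. General formula.** If a share w of episodes worsens, with s later-day steps each, then

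record-based rate = episode-based rate × (1 + w × s).

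**Step 3. Illustration for one induction arm.**
- Subjects: 53 per group (SAP 2.4).
- Exposure per subject: SAP 10.2.4 takes last dose plus 70 days minus first dose. With the last induction dose at Week 10 this is 70 + 70 = 140 days, assuming all doses are given.
- Patient-years: 53 × 140 / 365.25 = 20.3.
- Episodes: 100 (assumption). Episode-based rate: 100 × 100 / 20.3 = 492.6 per 100 patient-years.

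| w (assumed) | s (assumed) | Records | Rate per 100 patient-years | Increase |
|---|---|---|---|---|
| 5% | 1 | 105 | 517.2 | 5% |
| 10% | 1 | 110 | 541.9 | 10% |
| 20% | 1 | 120 | 591.1 | 20% |
| 30% | 2 | 160 | 788.2 | 60% |

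**Step 4. Comparison between arms**, with equal episodes and exposure per arm and s = 1. The rate ratio, ABBV-154 to placebo, is (1 + w in the ABBV-154 arm) / (1 + w in the placebo arm):
- 10% and 10%: 1.10 / 1.10 = 1.00
- 5% and 20%: 1.05 / 1.20 = 0.875
- 20% and 5%: 1.20 / 1.05 = 1.143

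**Step 5. A small-count extreme.** Suppose one infection yields three serious records with different start days and one preferred term. The serious-infection AESI rate for the arm is then 100 × 3 / 20.3 = 14.8 per 100 patient-years, against 100 × 1 / 20.3 = 4.9 if counted once. All three records qualify because Appendix G defines this AESI as the serious subset of an infections query.

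**The case against.** The strongest reply is that this is a stated convention, not an error. Protocol 6.1 defines a worsening as a new AE, Protocol 7.7 includes worsened events among TEAEs, and SAP 10.2.4 counts TEAEs with a prespecified rule. The documents agree with each other. That stands: the arithmetic is sound and nothing is contradictory. The weakness is that the resulting rate is not labelled as a count of records and will be read as incidence.

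The second reply is that other displays limit the harm. Subject percentages are shown, and SAEs, AEs leading to discontinuation and AESIs are listed, so a rate driven by one subject can be traced. This also stands, but it leaves the rate itself unchanged.

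The third reply is that the size rests on assumed shares, and that no hypothesis test on AE rates is planned. Both are true.

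A reader might infer two stronger conclusions, and the documents support neither:
- **Every rate is inflated.** A Grade 1 to 2 to 3 course counts once in the Grade 3 or higher rate. Serious and discontinuation rates take only qualifying records, and a death cannot be multiplied. The systemic glucocorticoid AESI rests on adjudicated results (SAP Appendix G), so raw record counting cannot be assumed for it.
- **The comparison is biased against ABBV-154, or against placebo.** With equal worsening the ratio is 1.00, and nothing in the documents indicates a difference or its direction.

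The Operations Manual and the Product Safety SAP were not available and may hold a rule that links worsened records. The sponsor should check them first.

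**Conclusion.** The point holds within limits. Taken together, Protocol 6.1 and SAP 10.2.4 count one continuous episode once per later-day grade step in the any-TEAE, SOC/PT and non-adjudicated AESI rates. This requires that the steps start on different days and carry the same preferred term. The Grade 3 or higher, serious and discontinuation rates are touched only when two or more records of the episode qualify. Deaths and subject percentages are not touched.

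The size is unknown. The factor 1 + w × s gives 1.05 to 1.60 over the assumed values tabulated above. The between-arm ratio departs from its episode-based value only if w × s differs by arm. These are descriptive Phase 2 summaries and no efficacy conclusion depends on them. The change is worth making because it is cheap and lets the rate be read as a frequency of events.

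**What to change.** Leave data collection under Protocol 6.1 as it is. In SAP 10.2.4, define an episode-based count:

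- Treat consecutive records as one event when they share subject and preferred term, the later record has a higher grade, and it starts on, before or the day after the end of the preceding record.
- Date the event from its first onset within the analysis period and give it the maximum grade. An event that began before the period and worsens in it then still counts once there, in line with Protocol 7.7.
- Keep as separate events any episodes divided by a gap, and any concurrent records without a rise in grade. The grade condition prevents distinct concurrent events from being merged.
- Present the episode-based rate in the overview, SOC/PT and AESI tables. Keep the present count beside it, labelled as a record-based rate, for comparability.

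The cost is a few lines of SAP text and one programming step. The step relies on AE end dates, and the SAP has a rule for incomplete onset dates (10.2.1) but none for incomplete end dates, so one must be added. A worsened event coded to a different preferred term will not be linked. Episode-based rates will be somewhat lower than record-based ones, which is a reason to show both. The rule is best fixed before unblinded rates are produced.
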